##### **6.4.2.1        Radiographic PFS and Other Time-to-Event Endpoints**

The following secondary time -to -event endpoints will be analyzed using similar methods as those described for OS above:

- Time to cancer-related pain progression
- Time to first SSE
- rPFS
- Immune-modified rPFS
- Time to initiation or increased opiate analgesic use for cancer pain
- Time to PSA progression

Data for patients who do not have post-baseline information will be censored at the date of randomization plus 1 day. Data for patients who have not experienced an event at the time of the analysis will be censored at the last available assessment.

Hazard ratios and 95% CI from a stratified Cox proportional hazards model will be provided. Kaplan-Meier methodology will be used to estimate median time to event and the 95% CI will be provided. Analyses of rPFS will also include the rPFS rate at 6 and 12 months.

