Enzalutamide is an oral androgen receptor blocker that impacts receptor signaling at multiple steps, including competitive binding to the androgen receptor, inhibition of nuclear translocation, and consequently prevention of binding of the androgen receptor to relevant activation sequences in the nucleus. Enzalutamide demonstrated statistically significant improvement over placebo in the primary endpoint of OS in the post-docetaxel setting in mCRPC patients (18.4 vs. 13.6 months; HR=0.631,  $p < 0.0001$ ). Additionally, key secondary endpoints demonstrated statistically significant differences including rPFS, time to first skeletal-related event, and time to PSA progression (Scher et al. 2012). In a second pivotal study in the pre-docetaxel setting in asymptomatic and mildly symptomatic patients, enzalutamide demonstrated statistically significant improvement over placebo in the co-primary endpoints of rPFS (not yet reached vs. 3.9 months; HR=0.186;  $p < 0.0001$ ) and OS (32.4 vs. 30.2 months; HR=0.706;  $p < 0.0001$  [Beer et al. 2014]). Other key secondary endpoints, which supported the rPFS and OS data, included time to first skeletal-related event, time to

initiation of cytotoxic chemotherapy, and time to PSA progression. Rates of fatigue and hypertension were higher in the enzalutamide groups in both studies. Seizures were reported in less than 1% of patients receiving enzalutamide.

Radium-223 dichloride is an alpha-emitting calcium mimetic radioisotope, which localizes to bone forming regions of cancer metastases (Parker et al. 2013). It is an applicable treatment for symptomatic patients without visceral disease. Radium-223 was compared to placebo in patients with symptomatic mCRPC with bone-only disease and demonstrated significant improvement in the primary endpoint of OS (14.9 vs. 11.3 months; HR=0.70;  $p < 0.001$ ); additionally, the key secondary endpoint of time to first symptomatic skeletal-related event was similarly improved (15.6 vs. 9.8 months; HR=0.66;  $p < 0.001$ ). Radium-223 dichloride was associated with low myelosuppression rates and fewer adverse events than the placebo group.

Despite recent advances in the treatment of prostate cancer described above, patients with mCRPC experience significant morbidity and mortality related to their disease and the median life expectancy from time of first metastatic diagnosis remains less than 3 years.

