
 
•To evaluate the efficacy of atezolizumab/enzalutamide compared with enzalutamide alone
 
	
 
•OS probability at 12 and 24 months
 
•Time to first SSE An SSE is defined as external beam radiation therapy to relieve skeletal symptoms (including initiation of radium-223 dichloride or other types of radionuclide therapy to treat symptoms of bone metastases), new symptomatic pathologic bone fracture, clinically apparent occurrence of spinal cord compression, or tumor related orthopedic surgical intervention.
 
•rPFS, as assessed by the investigator, and adapted from the PCWG3 criteria (Scher et al. 2016; see Appendix 2). rPFS is defined as the time from randomization to the earliest occurrence of one of the following: A patient is considered to have progressed by bone scan if: The first bone scan with <math>\geq 2</math> new lesions compared to baseline is observed <math>< 12</math> weeks from randomization and is confirmed by a second bone scan taken <math>\geq 6</math> weeks later showing <math>\geq 2</math> additional new lesions (a total of <math>\geq 4</math> new lesions compared to baseline); the date of progression is the date of the first post-treatment scan, OR After the first post-treatment scan, <math>\geq 2</math> new lesions are observed relative to the first post-treatment scan, which is confirmed on a subsequent scan <math>\geq 6</math> weeks later; the date of progression is the date of the post-treatment scan when <math>\geq 2</math> new lesions were first documented.
 
Progression of soft tissue lesions, as defined per PCWG3 modified RECIST v1.1
 
Death from any cause
 

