### **6.1 DETERMINATION OF SAMPLE SIZE**

A total of approximately 730 patients are planned to be enrolled in the global phase of this study: 10 patients during the non-randomized safety run-in phase, and approximately 720 during the randomized phase of the study.

The sample size of 10 patients for the safety run-in is based on clinical considerations. No statistical hypothesis tests will be performed on data from the safety run-in phase.

The final analysis of the primary endpoint of OS will be performed when approximately 540 deaths have occurred in the ITT population (75% of 720 patients).

The calculations are based on the following assumptions:

- Log-rank test
- 1:1 randomization
- Two-sided alpha of 0.05
- Median OS for the control (enzalutamide alone) arm of 12 months and estimated median OS in the experimental arm of 16.7 months, corresponding to a HR of 0.72
- A drop-out rate of approximately 5% per 2-year period
- One interim OS analysis

It is projected that an observed HR of  $\leq 0.84$  will result in a statistically significant difference between treatment arms (i.e., the HR of 0.84 will be the minimally detectable difference at the final analysis). This corresponds to an improvement of median OS from 12 months to 14.3 months.

In case of proportional hazards, 540 events would provide 97% power to detect a difference in the duration of OS given the above assumptions. However, computer simulations show that the actual power of the log-rank test is likely lower in case of control patients switching to subsequent lines of immunotherapy following progression. For example, if 15% of control patients receive subsequent treatment providing similar OS benefit as atezolizumab, the reduction in power is projected to be approximately 6%.

Recruitment of the planned 720 patients is projected to be completed within 13 months. On the basis of the above assumptions, the required number of OS events for the final analysis is projected to occur at approximately Month 38 after randomizing the first patient.

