#### **6.4.2            Secondary Efficacy Endpoints**

Analyses of the primary endpoint of OS and the key secondary efficacy endpoints listed below will be performed in a hierarchical fashion with type 1 error control (see Section 6.8.1). The primary endpoint of OS will be analyzed first. If the null hypothesis for the OS endpoint is rejected, then the key secondary endpoints will be in the order provided:

1. Time to cancer-related pain progression
2. Time to first symptomatic skeletal event (SSE)
3. rPFS

If for one endpoint in this list the null hypothesis cannot be rejected, then the results for this and all following endpoints are not considered to be statistically significant. Analyses of other secondary endpoints of this study will be considered as descriptive in nature, and no formal hypothesis testing will be conducted.

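### Kaplan-Meier for time to first SSE censors SSE-free deaths, so its curve and median overstate how many patients have an SSE and how soon; the hierarchy test is unaffected

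*Combined protocol and SAP*

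**What the plan says.** Time to first SSE is second in the key secondary hierarchy of Section 6.4.2, behind pain progression and ahead of rPFS. Table 1 defines it by skeletal events only: "An SSE is defined as external beam radiation therapy to relieve skeletal symptoms", with radionuclide treatment, symptomatic fracture, cord compression and orthopedic surgery as the other components. Death is not among them. The rPFS definition in the same table does include death.

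Section 6.4.2.1 says that the secondary time-to-event endpoints "will be analyzed using similar methods as those described for OS above". Through Section 6.4.1 this brings in the stratified log-rank test and Kaplan-Meier plots. It then gives the censoring rule, "Data for patients who have not experienced an event at the time of the analysis will be censored at the last available assessment", and two summaries: "Hazard ratios and 95% CI from a stratified Cox proportional hazards model will be provided" and "Kaplan-Meier methodology will be used to estimate median time to event". Survival rates at fixed times are named for OS (12 and 24 months) and rPFS (6 and 12 months), but not for SSE.

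Section 6.1 assumes "Median OS for the control (enzalutamide alone) arm of 12 months" and sets the final analysis at about 540 deaths among 720 patients. No section mentions competing risks, cumulative incidence or a sensitivity analysis for SSE-free deaths.

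**The concern.** Kaplan-Meier treats a censored patient as someone who could still have the event later. A patient who has died cannot. With SSE-free deaths censored, the curve describes a hypothetical setting in which nobody dies before an SSE, and it does so only if death is independent of SSE risk. The protocol does not define or label such an estimand. A clinical reader will take the median as the time by which half the patients had an SSE, and one minus the curve as the proportion affected. In a population with a planned control median OS of one year, both readings are off, and always in the same direction.

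The absolute picture by arm is also at stake. SSE is formally tested only once OS is significant, which is when mortality is most likely to differ between arms. Patients who live longer have more time to accrue SSEs, and a Kaplan-Meier display with deaths censored does not show this.

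**Working it through.** **Plan's own mortality figure.** 540/720 = 0.75. Take exponential OS with medians of 12 and 16.7 months, uniform accrual over 13 months, and dropout hazard −ln(0.95)/24 per month. At Month 38 this gives about 293 control and 255 experimental deaths, 548 in all, against the stated 540 (+1.5%). The planned death hazards are therefore a fair starting point.

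**Direction.** Let s(t) be the SSE hazard and d(t) the hazard of SSE-free death, with cumulative hazards S(t) and D(t).
- With deaths censored, one minus Kaplan-Meier estimates ∫ s(u)·exp(−S(u)) du.
- The proportion who actually have an SSE is the cumulative incidence, ∫ s(u)·exp(−S(u) − D(u)) du.
- The second is smaller whenever D > 0. Constant hazards are needed only to put a size on the gap.

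**Inputs for the size.**
- Control death hazard: ln2/12 = 0.0578 per month (Section 6.1).
- SSE-free death hazard d: assumed at 50% to 100% of that value, because all-cause deaths include deaths after a first SSE.
- SSE hazard s: the protocol gives none for this population. The medians of "15.6 vs. 9.8 months" quoted in Section 1.1.1 for the radium-223 trial are used as an illustration: s = ln2/9.8 = 0.0707 and s = ln2/15.6 = 0.0444.

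**Formulas with constant hazards.** One minus KM = 1 − exp(−s·t). Cumulative incidence = s/(s+d) × [1 − exp(−(s+d)·t)].

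Worked case, SSE median 9.8 months, d at 100%, t = 24: one minus KM = 1 − exp(−1.697) = 81.7%. Cumulative incidence = 0.0707/0.1285 × [1 − exp(−3.084)] = 0.550 × 0.954 = 52.5%.

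Control arm:

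| SSE median (KM) | Month | 1 − KM | Cumulative incidence, d at 50% | d at 100% | Ratio |
|---|---|---|---|---|---|
| 9.8 | 12 | 57.2% | 49.5% | 43.3% | 1.16 to 1.32 |
| 9.8 | 24 | 81.7% | 64.5% | 52.5% | 1.27 to 1.56 |
| 15.6 | 12 | 41.3% | 35.5% | 30.7% | 1.16 to 1.35 |
| 15.6 | 24 | 65.6% | 50.2% | 39.7% | 1.31 to 1.65 |

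The 24-month gap is 15.4 points (65.6 − 50.2) to 29.2 points (81.7 − 52.5). If SSEs are rarer, with a median of 30 months, the 24-month values are 42.6% against 31.7% to 24.5%, a ratio of 1.34 to 1.74.

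**Median.** Cumulative incidence levels off at s/(s+d). It reaches 50% at −ln(1 − 0.5(s+d)/s)/(s+d), if at all.
- KM median 9.8 months: half of patients have had an SSE at 12.2 months (d at 50%) or 18.6 months (d at 100%).
- KM median 15.6 months: 23.8 months (d at 50%), or never (d at 100%, where the ceiling is 43.5%).

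**Experimental arm** (death hazard ln2/16.7), 24 months: 81.7% against 68.7% to 58.8%, and 65.6% against 53.9% to 45.1%. The ratios are 1.19 to 1.45.

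**Contrast between arms.** Give both arms the same SSE hazard (KM median 12 months) and set d to the full planned death hazard. Kaplan-Meier shows 75% in each arm at 24 months. Cumulative incidence is 46.9% in control and 52.8% in experimental. The hazard ratio of 1 is correct for the cause-specific hazard, but the display hides the extra SSEs among longer survivors.

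**The case against.** The strongest reply is that the plan makes no false statement. It names a hazard ratio and a median for SSE, with plots by reference to OS, and no SSE rate at a fixed time. A median with deaths censored is a recognised cause-specific quantity, and Section 1.1.1 itself reports the radium-223 SSE result as medians and a hazard ratio. This stands in part. The error lies in how the curve and median will be read, so adding an output and a label is enough, and dropping the Kaplan-Meier summary is not required.

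Three points limit the size, and all three stand.
- The 9.8 and 15.6 months come from symptomatic patients with bone-only disease. This trial excludes unstable bone lesions and asks for symptomatic lesions to be irradiated before treatment (Section 4.1.2).
- A reader might take the 75% as the share of patients lost to the competing event. It is all-cause mortality and includes deaths after an SSE. Under the assumptions above, 28% to 54% of control patients die SSE-free by an average follow-up of 31.5 months (38 − 13/2).
- In Appendix 1 the SSE mark appears to go no later than the treatment discontinuation visit. The table layout is damaged, so this is uncertain. If SSE collection does end there, fewer deaths fall within SSE follow-up and the gap is smaller. Counting later deaths as SSE-free would then also be wrong.

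Finally, Section 3.3 records closure of the study after a futility recommendation, and SSE is tested only if OS is significant. The formal test may therefore never be run. Any descriptive SSE summary under Section 6.4.2.1 remains open to the misreading.

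**Conclusion.** The point holds as a matter of description and interpretation. With SSE-free deaths censored, the planned curve overstates the proportion of patients with an SSE, and the planned median is earlier than the time by which half have had one. The direction needs no distributional assumption.

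The size is illustrative: about 1.3 to 1.7 times at 24 months in the control arm and about 1.2 to 1.5 times in the experimental arm. It rests on constant hazards, borrowed SSE medians and an assumed share of SSE-free deaths. It shrinks if SSE collection ends at treatment discontinuation.

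A reader might infer that the second step of the hierarchy is invalid. The documents do not support that. The test is a stratified log-rank test with a Cox hazard ratio. Censoring deaths there targets the cause-specific SSE hazard, so the test and its type I error stand. Nor do the documents plan an SSE rate at a fixed time that would itself be wrong. This is a cheap improvement and not a flaw in the trial's inference.

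**What to change.** In Section 6.4.2.1 and the SAP:
- Keep the stratified log-rank test and cause-specific hazard ratio as the hierarchy test.
- Keep the Kaplan-Meier median, labelled as a cause-specific quantity with deaths censored.
- Add the Aalen-Johansen cumulative incidence of first SSE at 12 and 24 months by arm. Count death during SSE follow-up as the competing event, and censor patients when SSE collection ends. State when that is.
- Add SSE-free survival (SSE or death) as a sensitivity analysis.
- Do the same for time to PSA progression, whose definition in Table 1 also leaves out death. Its follow-up end needs the same care, because Appendix 1 moves PSA testing to standard of care after treatment stops.

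The cost is a few extra outputs and a short SAP addition. Death dates are already collected for OS, and the tests do not change. The reported SSE incidence will be lower than the Kaplan-Meier curve suggests.

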#### **6.4.2.2 PSA Response Rates**

An estimate of the PSA response rate and its 95% CI will be calculated for each treatment arm using the Clopper Pearson method. The difference of PSA response rates and 95% CI between the two treatment arms will be estimated by use of the normal approximation to the binomial distribution.

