## **6.4 EFFICACY ANALYSES**

### **6.4.1 Primary Efficacy Endpoint**

The primary efficacy endpoint is OS, defined as the time from randomization to death from any cause. Data for patients who are not reported as having died at the date of analysis will be censored at the last date known to be alive. Data for patients who do not have post-baseline information will be censored at the date of randomization plus 1 day.

The primary comparison of OS between treatment arms will be based on a stratified log-rank test. The HR for death in the experimental arm compared with the control arm will be estimated using a stratified Cox regression model, and the 95% CI will be provided. The stratification factors will be the same as the randomization stratification factors; however, stratification factors may be combined for analysis purposes if

necessary to minimize small stratum cell sizes. Combination of stratification factors, if any, would be specified in the SAP prior to analysis. Values for the stratification factors will be as recorded in the IxRS at the time of randomization. Results from an unstratified analysis will also be presented.

Kaplan-Meier plots will be constructed to provide a visual description of the difference between the treatment and control arms. Kaplan-Meier methodology will also be used to estimate median OS for each treatment arm. Brookmeyer-Crowley methodology will be used to construct the 95% CI for the median OS for each treatment arm.

The OS rate at key timepoints (12 months, 24 months) will be estimated using Kaplan-Meier methodology, along with 95% CIs calculated using the standard error derived from Greenwood's formula. The 95% CI for the difference in OS rates between the two treatment arms will be estimated by use of the normal approximation method.

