#### **6.4.2.3 Objective Response Rate in Soft Tissue Lesions**

The analysis population for objective response rate (ORR) will be all patients in the ITT population with measurable soft tissue lesions at baseline.

ORR is defined as the proportion of patients who had a confirmed response in soft tissue lesions. An estimate of ORR will be calculated for each treatment arm, and its 95% CI will be calculated using the Clopper Pearson method. The CI for the difference in ORRs between the two treatment arms will be determined using the normal approximation to the binomial distribution.

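### PSA response, ORR and DCR differences are analysed without the randomisation strata: a valid interval, but slightly wider than necessary if the strata predict response

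*Combined protocol and SAP*

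**What the plan says.** For PSA response, Section 6.4.2.2 gives a Clopper-Pearson interval for each arm and then states that the difference between arms, with its 95% CI, "will be estimated by use of the normal approximation to the binomial distribution". For ORR, analysed in ITT patients with measurable soft tissue lesions at baseline, Section 6.4.2.3 states: "The CI for the difference in ORRs between the two treatment arms will be determined using the normal approximation to the binomial distribution". Section 6.4.3 applies the ORR method to DCR. None of the three sections names a stratification factor.

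For OS, Section 6.4.1 states: "The primary comparison of OS between treatment arms will be based on a stratified log-rank test". The hazard ratio comes from a stratified Cox model, and "The stratification factors will be the same as the randomization stratification factors", which may be combined if cells are small. It adds that "Results from an unstratified analysis will also be presented". Section 6.4.2.1 also specifies a stratified Cox model for the secondary time-to-event endpoints, including time to PSA progression.

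Sections 3.1 and 4.2 give the four binary randomisation factors: prior taxane for mCRPC, liver metastasis, LDH and worst pain. Section 6.4.2 places only OS, pain progression, first SSE and rPFS in the tested hierarchy and treats the other secondary endpoints as descriptive.

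**The concern.** Stratified randomisation balances the arms within strata. A crude difference benefits from that balance, but its usual standard error does not take credit for it. If response differs between strata, the reported interval is wider than the design warrants. For ORR the argument is slightly different. Permuted blocks do not guarantee balance within the measurable-disease subset, so stratifying would adjust for chance imbalance and remove between-stratum variation from the comparison.

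Descriptive status does not explain the choice. Time to PSA progression is equally descriptive, yet its hazard ratio is stratified. Two PSA endpoints in one trial are therefore handled differently, and no reason is given. At stake are a little precision and some consistency in reporting.

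**Working it through.** **Plan's own figures.** The plan states no interval width, power or precision for PSA response, ORR or DCR, so there is nothing to reproduce for these endpoints. The OS design does reproduce. With 540 events and HR 0.72, power is 96.6% to 96.8% (stated: 97%), and the critical HR is 0.840 (stated: 0.84).

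**Inputs from the documents.** About 720 patients randomised 1:1, so 360 per arm (Section 6.1). PSA response of 26.5% on enzalutamide after abiraterone, and response rates of about 10% to 15% after two prior lines (Section 1.1.2). Caps of about 50% without prior taxane and about 10% with liver metastases (Section 3.1), used here as prevalences.

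**Assumptions not in the documents.** Experimental-arm rates of 35% (PSA) and 25% (ORR); 144 measurable-disease patients per arm; LDH above ULN in 35%; pain score of 4 or more in 40%; independent factors; a common odds ratio per adverse factor of 1, 1.5, 2 or 3.

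**Step 1: two equal prognostic halves.** The share of variance lying between strata is (half the gap)² / [p(1−p)], with p(1−p) = 0.265 × 0.735 = 0.195.

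- 20% vs 33%: 0.065² / 0.195 = 2.2% of variance. The interval narrows by 1 − √(1 − 0.022) = 1.1%.
- 15% vs 38%: 0.115² / 0.195 = 6.8% of variance. The interval narrows by 1 − √(1 − 0.068) = 3.5%.

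**Step 2: planned half-widths.** The formula is 1.96 × √[pc(1−pc)/n + pt(1−pt)/n].

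- PSA, 26.5% vs 35%, n = 360: 1.96 × √[(0.1948 + 0.2275)/360] = 6.71 points.
- ORR, 15% vs 25%, n = 144: 1.96 × √[(0.1275 + 0.1875)/144] = 9.17 points.

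**Step 3: stratified half-widths over all 16 cells.** The variance becomes Σ w_k [p_ck(1−p_ck) + p_tk(1−p_tk)] / n, where w_k is the cell's share of patients. Cell rates follow a logistic model in the number of adverse factors, fixed to the arm mean. The last two columns simulate the Mantel-Haenszel difference with Sato variance, 4,000 runs per scenario.

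| Odds ratio per factor | PSA half-width (narrower by) | ORR half-width (narrower by) | Simulated width ratio, PSA | Simulated width ratio, ORR |
|---|---|---|---|---|
| 1 | 6.71 (0%) | 9.17 (0%) | 1.000 | 1.004 |
| 1.5 | 6.62 (1.3%) | 9.07 (1.0%) | 0.987 | 0.995 |
| 2 | 6.47 (3.6%) | 8.92 (2.7%) | 0.966 | 0.979 |
| 3 | 6.19 (7.8%) | 8.60 (6.2%) | 0.923 | 0.947 |

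The largest gain is 6.71 − 6.19 = 0.52 points for PSA and 9.17 − 8.60 = 0.57 points for ORR.

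**Step 4: validity.** Simulated coverage was 94.5% to 96.4% for the crude interval and 94.5% to 95.2% for the stratified one. The planned interval is therefore valid and at most slightly conservative. The simulation balanced every stratum 1:1. The design does not guarantee that in the ORR subset.

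**Step 5: sparse cells.** The smallest cells hold 0.5 × 0.1 × 0.35 × 0.4 × 360 = 2.5 expected patients per arm. Six of 16 cells fall below 5 per arm at n = 360, and eight of 16 at n = 144.

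**The case against.** The case for leaving the plan alone is respectable.

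- **Nothing hangs on the width.** These endpoints carry no alpha and no power claim. This stands.
- **The inconsistency is only partial.** For OS at 12 and 24 months the plan says: "The 95% CI for the difference in OS rates between the two treatment arms will be estimated by use of the normal approximation method". So the plan has a pattern: log-rank and Cox comparisons are stratified, and differences in rates are crude. This stands as a limit on the point. It does not explain why the plan stratifies a descriptive hazard ratio but not a descriptive difference in proportions.
- **The gain may be nil.** The documents give no response rate by stratum. Section 3.4.5 treats the factors as prognostic for mCRPC and suggests that prior taxane may weaken hormonal therapy, which makes some association with PSA response plausible. It does not quantify one. This stands, and the range above starts at zero for that reason.
- **Sixteen strata are too many.** True of the full cross, and with uninformative strata the ORR interval widened trivially (ratio 1.004). Pooling answers this. Section 6.4.1 already allows factors to be combined, although the text reviewed fixes no pooling rule.
- **It is late.** The synopsis and Section 3.3 record closure for futility. A change to the estimator in an open-label trial must be documented before the analysis or labelled post hoc. This stands, and it limits the remaining value to final reporting.

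A reader might go further and infer that the planned intervals are wrong, or that the binary endpoints are treated differently from everything done for OS. The documents support neither reading: the crude interval keeps its coverage, and the OS-rate differences are handled in the same way.

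**Conclusion.** This is a minor efficiency and consistency point. The PSA response, ORR and DCR differences are planned without the strata used in randomisation and in the log-rank and Cox analyses. The resulting interval is valid. If the strata predict response, it is wider than necessary by about 1% to 3.5% under the two-halves splits and by 0% to 8% over the wider assumed range, which is at most about 0.6 percentage points of half-width. If they do not, there is no loss. The size depends on assumed stratum effects, prevalences, experimental-arm rates and a measurable-disease subset of unstated size. DCR was not computed separately; it follows the ORR method. It would overstate the case to call the intervals needlessly wide or to suggest that any trial conclusion is affected.

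**What to change.** In Sections 6.4.2.2 and 6.4.2.3, and for DCR in Section 6.4.3, estimate the difference with Mantel-Haenszel weights and a stratified interval (Sato or Newcombe). Use the strata as recorded in the IxRS, under a pooling rule fixed in the SAP before analysis and identical to the one used for OS. Do not use the full 16-cell cross. Keep the crude difference as supportive, mirroring the OS plan, and state whether the OS-rate differences at 12 and 24 months stay unstratified.

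The cost is SAP wording and one further procedure call. The small downside is that the ORR interval may widen trivially where strata are uninformative or sparse. If the sponsor prefers the crude difference alone, one sentence giving the reason would settle the point.
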